4.1.3 Trial duration

Agitated behaviours in dementia are different from the core cognitive or functional outcomes most often studied in dementia. For a treatment for agitation in dementia to be useful in clinical practice, it needs to be effective quickly. The primary outcome for the trial will test 12 weeks of masked treatment. Data from preliminary studies and experience with mirtazapine and carbamazepine suggest that beneficial effects emerge within a 4 to 12 week time frame. Comparisons at these time points are important secondary questions. Although the trial will close in all sites following completion of assessments in all patients for the 12 week intervention, assessment of longer term effects of 12 weeks of treatment on CMAI, treatment status, institutional transition and death will be completed by means of telephone follow-up at 26 and 52 weeks.

4.1.4 Explanation for choice of comparator

Active treatments described above will be compared with matched placebo. Usual care will be provided to all patients in the trial. The use of placebo is justified as there is genuine uncertainty as to whether either of the active interventions will be better than no treatment. Treatment is blinded to reduce potential bias as the main outcome measures are patient reported outcomes.

4.1.5 Risks mitigation strategy

In this trial our primary concern is the safety of participants. There are risks to all medications, in the case of mirtazapine and carbamazepine these are well understood. Mirtazapine and carbamazepine have been widely prescribed, including to older adults in general and those with dementia for a number of years. Although agitation in dementia is a new indication, the side effects are expected to be the same as in the current versions of the SmPCs. As the trial is blinded we have considered the contraindications of both drugs when entering patients into the trial, and they are considered together here.

Our risk mitigation strategy includes the addition of actions that may not be part of routine clinical practice by community mental health services in the management of agitation in dementia with mirtazapine and carbamazepine. So, the doses of carbamazepine that will be used are low in comparison to the doses often used in epilepsy so dose-related side effects should be minimised. The mirtazapine dose is within the normal dosage range. These actions include the careful monitoring for harms including side effects and adverse events that is a core element of the study. However in addition we are adding a set of safety blood tests (FBC, U&Es & LFTs) and, ECG testing at baseline and at the study end. Gradual dose escalation will also be used to help to minimise side effects.

The IMP in this trial is contraindicated in patients with second degree atrioventricular block (first degree AV block, and third degree where the patient has a pace maker fitted, may be acceptable, at the discretion of the principal investigator, having reviewed the ECG trace). Also contraindicated are a history of bone marrow depression or history of hepatic porphyrias as per the SmPC for carbamazepine and these are reflected in the exclusion criteria.

The blood tests and the ECG will help us to give careful consideration and to instigate monitoring if needed to patients with; moderate to severe renal impairment (creatinine clearance <40ml/min), hepatic impairment, cardiac diseases (such as conduction disturbances, angina pectoris and recent myocardial infarction), low blood pressure, diabetes and any other conditions as listed in the current versions of the SmPCs. Decreased platelet or white blood cell counts occur occasionally to frequently

in patients taking carbamazepine. Blood counts including platelets and reticulocytes will be taken at baseline and after 12 weeks of dosing. Further blood tests may be ordered during the trial if clinically indicated.

There is a well-recognised risk of drug interactions which will be managed by increased monitoring or through exclusion of some categories of drugs, as listed in the exclusion criteria.

An increase in suicidal thoughts has been observed as a rare effect in the early stages of treatment with antidepressants. We have therefore included the Columbia Suicide Severity Rating Scale (C-SSRS) at baseline and at the 6 and 12 week assessment timepoints to monitor this, again the PI will have access to these data following baseline assessment and from subsequent visits. Hyponatraemia is also a recognised rare side effect of antidepressant medication and the baseline and 12 week U&Es will allow us to monitor this.

4.2 **Objectives**

The overall trial aim is to assess the safety, clinical and cost effectiveness of mirtazapine and carbamazepine in the treatment of agitation in dementia.

The null hypothesis is that there is no difference in CMAI scores between patients treated with placebo and mirtazapine, and between patients treated with placebo and carbamazepine, at 12 weeks.

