5.3.4 Participant Timeline

Assessment	Baseline ^c	Rx 'week 0' visit (0-7 days after baseline)	Week 2 (12-16 days after randomisation)***	Week 4 (21-35 days after randomisation)***	Week 6 (35-49 days after randomisation) ^c	Week 12 (77-91 days after randomisation) ^c	Week 16 (105-119 days after randomisation)***	Week 26* (wk 25- 27)	Week 52* (wk 51- 53)
Consent	х								
Cohen Mansfield Agitation Inventory CMAI (Long form)	x				X	x			
Safety Bloods FBC, U&Es, LFT	Xª					Xp			
Electrocardiogram (ECG)	Xa					Xp			
Client Service Receipt Inventory CSRI**	Х				X	X			
Disease specific Quality of Life DEMQOL	X				Х	x			
Carer assessed disease specific Quality of Life DEMQOL-Proxy	x				Х	X			
Generic Quality of Life EQ-5D-5L (Proxy)	х				x	X			
Cognitive impairment sMMSE	x				x	Х			
Behavioural and psychological	Х				x	Х			

symptoms in dementia									
BPSD-NPI									
Columbia Suicide	Х				х	х			
Severity Rating Scale									
C-SSRS (Cognitively									
impaired version)		V							
Randomisation		х							
Dispensing		Х			х				
Adherence			Х	X	Х	х			
Adverse events			Х	Х	Х	х	Х		
Medication assessment (for dose changes)			X	X	X				
Use of rescue medications					X	X			
Concomitant medications	Х	X	X	X	X	x			
Withdrawal of treatment			X	X	x	x			
Carer mental health GHQ-12 ^d	Х				x	x			
Carer quality of life EQ-5D-5L ^d	X				X	x			
Carer burden index Zarit CBI ^d	Х				X	X			
Carer proxy report of CMAI score***								Х	Х

Carer proxy report of treatment***				Х	X
Institutionalisation***				Х	Х
Death***				Х	Х

* Longer term assessments will be undertaken by site research workers employed on the research grant whilst the research sites remain open, and by Centre of Dementia Studies (CDS) staff at BSMS when the sites have closed.

**Medication and health service use may also be accessed from GP records by research workers.

*** At weeks 2, 4, 16, 26 and 52, carers will be contacted by telephone. All other visits will take place in the patient's place of residence, unless the patient requests otherwise.

^a May utilise existing results (if available) up to 28 days prior to randomisation date.

^b Ideally these tests would be done at week 12 visit, but may be done up ±14 days after last dose of study medication if required.

^c Face-to-face visits may take place over more than one visit if required, particularly if blood/ECG tests are to be collected.

^d Asked of unpaid carers only.

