5.3.5.4 Two and four week medication assessment calls

Two weeks after the patient takes their first trial medication the research worker will phone their carer to discuss their treatment. The call will follow a structured written pro forma that will record details of adherence to medication prescription, changes to concomitant medications and reports of any adverse effects. Carers of patients without limiting issues including toxicity will be instructed to increase the trial medication by one capsule to two capsules. Where limiting issues are reported, the dose of trial medication prescribed should remain the same or the patient should be taken off trial medication. This will be determined by the site PI who will discuss all such cases with the research worker who will then feed back to the carer. This procedure will be repeated another 2 weeks later (four weeks after the patient takes their first trial medication), with a similar assessment to inform whether a patient should be dose escalated to a further capsule daily (maximum of 3 capsules daily), remain on the current dose, or be dose reduced or taken off trial medication as appropriate.

In the absence of side effects, clinical judgement will determine whether or not to escalate the trial medication dose or to remain on the current dose. A balanced consideration will take into account the fluctuating nature of symptoms of agitation over the disease course, the perspective of the carer and patient, and the potential negative impact on the results of the study and their interpretation if a large proportion of patients do not take the higher dose of trial medication. It is important that within the constraints of the trial emphasis is placed on reaching a therapeutic effect that can be generalised to a wide population.

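### The C-SSRS, added for a risk early in antidepressant treatment, is first repeated at week 6, after both dose-escalation calls; cover before then is general, not targeted

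*Protocol*

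**What the plan says.** Section 4.1.5 (Risks mitigation strategy) gives the reason for the scale: "An increase in suicidal thoughts has been observed as a rare effect in the early stages of treatment with antidepressants". It then presents the C-SSRS as the consequence, to be used "at baseline and at the 6 and 12 week assessment timepoints to monitor this", and adds that "again the PI will have access to these data following baseline assessment and from subsequent visits".

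The C-SSRS row of the schedule in section 5.3.4 marks the same three points and is blank at weeks 2 and 4. The relevant columns read "Week 2 (12-16 days after randomisation", "Week 4 (21-35 days after randomisation" and "Week 6 (35-49 days after randomisation" (closing brackets omitted).

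Sections 5.4 and 5.4.1 start patients on one capsule, expect two from week 2 and three from week 4, and allow no escalation assessment after week 4. Section 5.3.5.4 places both decisions at telephone calls to the carer: "The call will follow a structured written pro forma". The topics listed for it are adherence, changes in other medication, and adverse effects. The pro forma itself is not in the protocol.

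Other provisions that bear on the period before week 6:
- Section 5.3.5.4: limiting issues are decided by the site PI, and clinical judgement governs escalation when there are no side effects.
- Section 5.3.5.3: the carer keeps a diary card that includes side effects.
- Section 5.4.3: usual care includes key-worker case management and team review.
- Sections 5.1.1 and 5.4.9: the clinical team may change the dose or withdraw the patient.
- Section 5.10.2.1: the adverse-event definition is broad.
- Section 5.3.1.2: patients with a suicide risk are excluded at entry.

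**The concern.** The protocol describes this hazard by its timing, and it chose a dedicated scale in addition to general adverse-event questioning. Yet the scale is not used on treatment until about the middle of the 12 weeks. At both points where the dose may be raised, the latest scheduled C-SSRS available to the PI is the one taken before treatment.

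Suicidal thoughts are internal. The participants have dementia, and section 5.3.6 expects some to lack capacity. A general question to a carer about side effects may not bring out a change that the carer has noticed but does not regard as a drug effect. What is at stake is recognising such a change before a dose increase. The efficacy analysis is not involved.

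**Working it through.** The plan states no figure for this gap, so there is nothing to reproduce. The check is day arithmetic on the visit windows.

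**Inputs, in days after randomisation**
- Week 2 call: 12 to 16, nominal 14 (5.3.4 and 5.4.1).
- Week 4 call: 21 to 35, nominal 28 (5.3.4). Section 5.4.1 gives day 24 to 32; it names no origin, and randomisation is assumed here.
- Week 6 visit: 35 to 49, nominal 42 (5.3.4).
- Treatment length: 12 weeks = 84 days (1.3).

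**Gap from call to first repeat C-SSRS.** Minimum = earliest week 6 day − latest call day. Maximum = latest week 6 day − earliest call day.
- From week 2: nominal 42 − 14 = 28; range 35 − 16 = 19 to 49 − 12 = 37 days.
- From week 4, 5.3.4 window: nominal 42 − 28 = 14; range 35 − 35 = 0 to 49 − 21 = 28 days.
- From week 4, 5.4.1 window: range 35 − 32 = 3 to 49 − 24 = 25 days.

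No gap is negative. Within the schedule's windows the first repeat never comes before either escalation call; at the extreme it shares a day with the second. So 0 of the 2 escalation assessments follow a scheduled post-baseline C-SSRS. Week 6 also carries a mark for medication assessment in the 5.3.4 table, but 5.4.1 makes week 4 the last point for escalation.

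**Position within treatment**
- Counted from randomisation: 35/84 = 42% to 49/84 = 58%, nominal 42/84 = 50%.
- Counted from first dose: the table places the dispensing visit as a "visit (0-7 days after baseline" and marks randomisation and dispensing in that same column. The lag from randomisation to first dose is therefore not stated. Assuming 0 to 7 days, the first repeat falls on treatment day 35 − 7 = 28 (28/84 = 33%) to 49 − 0 = 49 (58%), nominally day 42 − 7 = 35 to 42.

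**Content of the calls.** The topics listed in 5.3.5.4, and the shorter list in 5.4.1, include adverse effects in general. Neither names suicidality.

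**The case against.** The strongest reply is that the text and the table agree on the timepoints, so the plan contains no contradiction, and that monitoring is layered. The first part is true. However, agreement between text and table does not settle whether the timepoints serve the stated purpose.

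Of the rest, the following stands:
- The call pro forma is not shown and may already ask about suicidality. If it does, there is no gap in practice, only in the protocol's description.
- Section 4.1.5 does not say how long the early stages last. Nothing in the protocol shows that weeks 2 to 4 are the critical period, or that week 6 is too late.
- The amendment log (8.2) records that the regulator asked for the C-SSRS. It does not say who chose the timepoints.
- One telephone question to a carer is a weaker instrument than the scheduled scale, and its added yield cannot be estimated from the protocol.

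Three stronger readings are tempting and not supported. A reader might infer that patients go unmonitored until week 6, or that detection rests only on what a carer happens to volunteer. The diary card, key-worker and team review, and the clinical team's powers over dose and withdrawal all apply in that period, and new suicidal talk would fit the adverse-event definition. A reader might also infer that raising the dose raises the risk. The protocol ties the risk to early treatment, not to dose, and describes the mirtazapine dose as within the normal range. Finally, the exclusion of patients with a suicide risk lowers the starting risk, but it cannot address thoughts that first arise on treatment.

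**Conclusion.** The point holds as a modest participant-safety weakness. The one targeted measure is first repeated nominally 28 days after the first escalation call and 14 days after the second, and until then cover is general. These are gaps in one instrument, not periods without monitoring.

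The day counts rest on the 5.3.4 windows. The figures counted from first dose rest additionally on the assumed lag of 0 to 7 days. The protocol calls the effect rare and gives no event rate, so the number of cases that might be recognised late cannot be estimated. The primary estimate, power and type I error rate are unaffected. The change is worth making because it is cheap and brings the schedule closer to the protocol's own reason for the scale.

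**What to change.** In section 5.3.5.4 and the 5.3.4 schedule, add one carer-reported question on new suicidal talk or behaviour to the week 2 and week 4 calls. Refer any positive answer to the site PI before any dose increase, through the existing route for limiting issues. Keep the C-SSRS at baseline, week 6 and week 12. If the pro forma already contains such a question, only the protocol text needs to change.

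The question must go to all arms because the trial is blinded, although only 157 of the planned 471 patients are in the antidepressant arm. The load is at most 471 × 2 = 942 calls, or 942/8 ≈ 118 per centre. At an assumed 1 to 2 minutes each, that is 942/60 = 15.7 to 1,884/60 = 31.4 hours over the whole trial, with no new visit or staff. Further costs are a small form and database change, briefing of research workers, PI time for positive answers, and amendment approval if needed. The limitation to accept is that carer report is less sensitive than the full scale.

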5.3.5.6 Week 12 home visit

At this visit the full range of assessments described in the table of assessments in section 5.3.4 of the protocol will be performed. Safety bloods and an ECG will be taken, if necessary the bloods may be collected at a separate visit, as per baseline blood collection. Bloods and ECG should take place within ±14 days of study drug discontinuation.

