5.10.2.3 Other Notifiable Adverse Events

A notifiable event in this trial is grade 3 (or higher) haematological toxicity (according to CTCAE criteria), identified in any routine blood tests conducted whilst the patient is taking trial medication, including the protocol specified week 12 blood tests. These events should be reported to NCTU using the standard SAE form.

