5.10.2.5.2 Severity or grading of Adverse Events

The severity of all AEs and/or ARs (serious and non-serious) in this trial is based on the Research Worker and site PI's clinical judgement.

For general (eg: non-haematological) AEs/ARs, they should be graded using the following definitions:

1 – Mild: An event that is easily tolerated by the participant, causing minimal discomfort and not interfering with every day activities.

2 – Moderate: An event that is sufficiently discomforting to interfere with normal every day activities.

3 – Severe: An event that prevents normal every day activities

For haematological (eg: from blood test results) AEs/ARs, they should be graded using the Common Terminology Criteria for Adverse Events v4.03 (CTCAE) June 14, 2010 criteria using the following definitions:

Grade 1:	Mild; asymptomatic or mild symptoms; clinical or diagnostic observations only;
	intervention not indicated.

- Grade 2: Moderate; minimal, local or non-invasive intervention indicated; limiting ageappropriate instrumental ADL*
- Grade 3: Severe or medically significant but not immediately life threatening; hospitalisation or prolongation of hospitalisation indicated; disabling; limiting self-care ADL**
- Grade 4: Life threatening consequences; urgent intervention indicated.
- Grade 5: Death related to AE

A semi colon indicates 'or' within the description of the grade.

* Instrumental Activities of Daily Living (ADL) refer to preparing meals, shopping for groceries or clothes, using the telephone, managing money etc.

** Self care Activities of Daily Living (ADL) refer to bathing, dressing and undressing, feeding self, using the toilet, taking medications and not bed-ridden.

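### The rules that act on the safety bloods say 'haematological', so a severe sodium or liver result is not clearly notifiable or CTCAE-graded, although section 4.1.5 relies on the U&Es to monitor hyponatraemia

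*Protocol*

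**What the plan says.** - **Risk and monitoring.** Section 4.1.5 adds FBC, U&Es and LFTs at baseline and at study end. It names reduced platelet or white cell counts on carbamazepine, and hyponatraemia as a rare effect of antidepressants. For the latter, "the baseline and 12 week U&Es will allow us to monitor this".
- **Notification.** Section 5.10.2.3 makes notifiable, on the SAE form, "grade 3 (or higher) haematological toxicity (according to CTCAE criteria), identified in any routine blood tests conducted whilst the patient is taking trial medication". It then expressly adds the week-12 bloods.
- **Grading.** Section 5.10.2.5.2 has two scales. One reads "For haematological (eg: from blood test results) AEs/ARs, they should be graded using the Common Terminology Criteria for Adverse Events". The other reads "For general (eg: non-haematological) AEs/ARs, they should be graded using the following definitions"; its lowest level is an event that is easily tolerated, "causing minimal discomfort and not interfering with every day activities". Grade 3 on the printed CTCAE scale begins "Severe or medically significant but not immediately life threatening".
- **Sampling window.** Section 5.3.5.6 says "Bloods and ECG should take place within ±14 days of study drug discontinuation". The schedule footnote in 5.3.4 says that the tests "may be done up ±14 days after last dose of study medication if required".
- **Surrounding safety net.** Section 5.10.2.1 counts abnormal laboratory results as adverse events and runs SAE reporting to 4 weeks after the last dose (5.10.2.6.1 says 30 days). Its notes on important medical events give blood dyscrasias without hospital admission as an example.

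**The concern.** Section 4.1.5 treats the U&Es as the means of monitoring a named electrolyte risk. A result protects participants through the rule that says what a site does with it. The notification rule puts a severe laboratory value on an SAE form without leaving that step to local judgement. If it is worded for blood counts only, the one electrolyte risk that the protocol names is not clearly on that route, and liver results are not either.

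The grading rule has the same weakness. The general scale looks at discomfort and everyday activities and has no term that responds to the laboratory value itself. A marked fall in sodium without symptoms could be entered as mild by one site and CTCAE-graded by another, with both following the text.

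A second, smaller mismatch lies in timing. Bloods may be taken after the last dose, while the notification rule speaks of tests on drug and the week-12 bloods. Participants taken off treatment for side effects are among those most likely to be sampled after stopping.

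**Working it through.** No formula tests this point. The check sets the sections side by side.

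**1. Which panels does the term cover?** The scheduled bloods are three: FBC, U&Es and LFTs (4.1.5; schedule in 5.3.4). In its plain sense 'haematological' describes the FBC. Sodium is in the U&Es and is biochemistry, as are the LFTs. So 3 − 1 = 2 of the 3 panels lie outside the plain term.

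**2. Notification (5.10.2.3).** The rule uses the term with no gloss. On the plain words, a grade 3 or higher sodium or liver result is not notifiable unless it also meets the SAE definition.

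**3. Grading (5.10.2.5.2).** Here the term carries a bracket pointing to blood test results. Two readings are open:
- Plain: sodium is non-haematological, goes to the three-level general scale, and a symptom-free fall is mild.
- Wide: sodium is a blood test result, goes to CTCAE, and may reach grade 3, whose printed description includes medical significance.

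The text does not settle which applies. The log of changes in section 8.4 speaks of blood AEs in general and ties the new grading to the regulator's request for blood safety tests. That points to the wide reading as the purpose, but a site works from the operative sections.

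**4. Timing.** Only the notification rule has an on-drug limit; the grading rule has none.

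| Rule | Time covered after the last dose |
|---|---|
| Accepted sampling (5.3.5.6; footnote in 5.3.4) | up to 14 days |
| Laboratory notification (5.10.2.3) | none by the on-drug wording; the week-12 bloods are added |
| SAE reporting (5.10.2.1) | 4 weeks = 4 × 7 = 28 days |
| SAE notification (5.10.2.6.1) | 30 days |

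For a participant who completes treatment, the end-of-treatment sample is the week-12 blood test and is covered. For a participant who stops early and is sampled within the 14 days that follow, well before week 12, the sample is off drug. It is covered only if it counts as the week-12 test under another date, which the text does not say.

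**5. What remains in place.** Section 5.10.2.1 makes the result an adverse event; 5.10.2.5 requires non-serious events to be recorded; 5.10.2 gives the IDMC unblinded frequencies of non-serious events by arm. A low sodium is therefore recorded and seen in aggregate. What is uncertain is its grade and whether it is notified promptly.

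**The case against.** The strongest reply is that the meaning can be recovered. The bracket in 5.10.2.5.2 and the amendment log both speak of blood results at large, so a careful site would apply CTCAE to sodium. This stands as evidence of intent and is the reason why the point is minor. It does not settle the matter, because the bracket is absent from 5.10.2.3 and the companion scale is expressly for non-haematological events.

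On early stoppers, the ±14-day sentence sits under the week-12 visit, so a sample taken under it may be meant as the week-12 test. In addition, blood dyscrasias are a listed example of an important medical event, and SAEs are reported for 4 weeks after the last dose. Both points stand, and a severe low count after stopping is therefore largely caught. No electrolyte event is among the examples, so the backstop is weaker for sodium.

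A reader might infer more, and the documents do not support it:
- *That grading is also limited to results on drug.* The grading rule has no such limit.
- *That hyponatraemia is not monitored, or is hidden from the IDMC.* Abnormal results are recorded and non-serious frequencies are reviewed by arm.
- *That inconsistent grading distorts the comparison of arms.* Section 5.9.4.2 reports specific events descriptively and tests only the prevalence of patients with SAEs; no planned comparison uses severity grade. Sites are blinded and allocation is stratified by region.
- *That a particular sodium value is grade 3.* The protocol prints only the general CTCAE descriptions, and its Grade 1 also mentions findings without symptoms. No sodium cut-off is given.

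**Conclusion.** The point holds as a defect of wording in two safety rules. The term used covers one of the three scheduled blood panels in its plain sense, while section 4.1.5 relies on one of the other two for a named risk. The wider meaning was probably intended but is not written where sites will apply it. The timing mismatch is real but secondary, is confined to the notification rule, and is partly covered by the SAE rules.

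Its size cannot be put as a number of missed events, because the protocol gives neither a rate of severe sodium or liver results nor a rate of early stopping. The efficacy analysis is unaffected. So are the planned comparisons between arms, provided that a notifiable result sent on an SAE form is counted as an SAE only when it meets the seriousness definition. This is a cheap improvement to make with the next amendment.

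**What to change.** - **Section 5.10.2.3:** make notifiable any grade 3 or higher laboratory toxicity (CTCAE v4.03) in FBC, U&Es or LFTs, found in any blood test from first dose until 4 weeks after the last dose. Keep the present mention of the week-12 bloods, so that someone who stopped before week 8 (12 − 4) and is sampled at week 12 stays covered.
- **Section 5.10.2.5.2:** replace 'haematological', with its bracket, by 'laboratory (FBC, U&Es, LFTs)', and 'non-haematological' by 'non-laboratory'.

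The cost is two wording changes, a note to sites, and a few more SAE forms for severe sodium or liver results. No extra blood draw or visit is needed.
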